6. SAFETY

6.1. Adverse Event Reporting

Any adverse events in this study related to the use of dried blood spot specimens with the 4th generation EIA test will be recorded by the NSW State Reference Laboratory for HIV and the Project Coordinator at SHIL, and de-identified data on the event will be reported to the ethics review committee responsible for the pilot program overall. De-identified data relating to adverse events will also be reported by the Reference Laboratory and Project Coordinator to the principal investigators for discussion and review by the DBS pilot steering and working group at group regular meetings during the pilot period.

The psychological and physical wellbeing of pilot participants will be prioritised during the management of any adverse event. Complaints regarding the pilot will be managed by the Project Coordinator and de-identified data on the complaint will be reported to the principal investigators and ethics committee. Participants will be provided with the contact details of the Project Coordinator should they wish to make their complaint. The process of handling complaints will be conducted in accordance with Chapter 5.6 of the *National Statement on Ethical Conduct in Human Research, 2007* (31).

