4. PARTICIPANT SECTION

4.1. INCLUSION CRITERIA

Broad inclusion criteria for both Phase 1 and 2

- Individuals aged 16 years or older who reside in NSW
- Ability to provide independent informed consent to participate in the program, including consent to the provision of a dried blood spot sample for HIV and/or HCV testing, willingness to be contacted after consent to complete follow-up evaluation of their experience using DBS, and willingness to participate in and comply with the pilot program, namely the completion of registration details.

Inclusion criteria for DBS self-sampling HIV testing

Individuals who self-select as belonging to one of the following risk groups:

- men who have sex with men
- people who have a transgender history (or their current or previous partners)
- People from regions of high HIV prevalence*
- People whose current or previous sexual partners are from one of the above groups

*For the purposes of this study, this is considered to be countries within Africa and Asia or the following specific countries: Belize, Haiti, Bahamas, Jamaica, Guyana, Barbados, Suriname, Djibouti, Russian Federation, Trinidad and Tobago and Panama.

Inclusion criteria for DBS self-sampling HCV testing

Individuals who self-select as belonging to one of the following risk groups:

- People who identify as Aboriginal or Torres Strait Islander;
- People who have ever injected drugs
- People that are currently or have ever been incarcerated
- People who are or have been clients of community corrections services
- People who are using or have used drug and alcohol services or mental health services
- People who are or have been homeless
- People from Africa or the Middle East or regions of high HCV prevalence**

** For the purposes of this study, this is considered to be any country where the participant or their parents were born overseas or a language other than English is spoken in the home.

A key modification to protocol version 3.0, approved by the DBS Steering Committee and Principal Investigators, is the HIV and HCV tests will be separated out and offered to individuals based on meeting the eligibility criteria for each test.

For settings-based DBS testing (phase 2), settings will be able to provide DBS testing kits to participants who meet the eligibility criteria where they also access a service for which any of the following situations may apply:

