5.11. VENEPUNCTURE SUBSTUDY

At selected clinics, participants will be asked to provide a paired sample of blood (5ml) collected via venepuncture by a healthcare professional. This will be optional for participants. Up to 1300 participants will be enrolled in the venepuncture sub study. Participants can take part in the DBS HIV and HCV study without providing this sample. The primary objective of this sub-study is to compare the analytical performance of DBS as a sample type for the diagnosis of hepatitis C (antibody and RNA) to standard of care (venous-collected samples). All samples will be tested at NSW Health Pathology laboratories. Results delivery will be as per standard of care by NSW Health Pathology to the service ordering the tests. Participants will not receive HCV treatment as part of this study. Participants that are RNA positive will be linked to standard of care to assess for HCV treatment eligibility. Reactive DBS hepatitis C results will not need a confirmatory test as the sample will be paired to a venous sample tested as per standard of care. See Appendix D.

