5.12. LABORATORY TESTING PROCEDURES

Once the package is received at the NSW State Reference Laboratory for HIV, the sample will be processed then tested. HIV testing will use one of the Abbott Alinity i automated anaylser, HIV antigen/antibody combo assay. HCV testing will use the Hologic Panther, Aptima HCV Quant Dx assay which is an in vitro nucleic acid amplification test (NAAT) performed on automated platforms. All DBS samples received by the laboratory will be tested according to a specific algorithm described below and in Appendix B (see Appendix B for the testing flowchart).

The HIV 4th generation EIA has a sensitivity of >99%, a specificity of >99% and window period of 15-21 days (26). Samples found reactive by EIA will have a Western Blot test conducted consistent with routine practices. Trial data suggests the Aptima HCV NAAT has a specificity of 98.6%, and is highly sensitive (27).

All commercially available laboratory tests for HIV are not intended for use with DBS samples. HIV testing is highly regulated in Australia by the TGA and application of in-vitro diagnostic devices with alternate sample types not supported by the manufacturer involves using the product 'off-label' under the Therapeutic Goods Administration's Clinical Trial Notification (CTN) Scheme.

Testing will be done frequently to ensure a fast turn-around time for receipt of results. The NSW State Reference Laboratory for HIV has successfully participated in an established external quality assurance scheme (EQAS) for HIV testing in Dried Blood Spot samples coordinated by the US Centers for Disease Control (CDC) for more than 20 years. It is anticipated that DBS samples received by the testing laboratory will be tested and results made available within one week. This would include confirmation of HIV reactive samples by HIV Western blot. The advantage of testing of samples in a reference laboratory allows for a variety of supplemental tests to be applied in the confirmation of true test positivity. This testing may also include TGA approved nucleic acid tests for HIV for which manufacturers have made claims to support the use of DBS sample types.

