As a way of ensuring the veracity of the sample sent to the laboratory, the participant will receive a validation code when registering for the study online. The validation code will be cross-checked prior to testing of the DBS sample and again before test results are released to the participant. If participants have lost their validation code they may also call the Sexual Health Infolink on [name] to retrieve this upon correct identification. If the individual is completing the DBS test with assistance from a trained worker, clinician or peer worker, a validation code is not required. Instead, the trained worker will enter the DBS kit code and their own contact details for third point of validation.

(ii) Inaccurate results dependent on the window period and sensitivity and specificity of the test The patient information sheet (attachment 1) and information provided on the DBS website will provide appropriate information required for informed consent. This will include how the test performs in comparison to conventional laboratory HIV or HCV testing, the limitations of the test including the window period, and the need for repeat testing if there has been a recent risk event or illness. Results of DBS samples found to be reactive will not be provided to the participant until a validated confirmatory test such as Western Blot has been conducted. Information will be provided on the registration website directing individuals to seek clinical review for Post-Exposure Prophylaxis (PEP) if they think they have had an exposure to HIV within the previous 72 hours.

- (iii) Bleeding, discomfort and bruising can occur from a finger prick test.
- (iv) Participants may experience stress and anxiety while waiting for their DBS HIV or HCV test result

- (v) Participants may feel embarrassed answering some of the questions in the client survey regarding sexual behaviour. However, this has been minimised by using an online format, enabling people to provide the information in the comfort of their own home or other private location
- (vi) Participants may experience stress and anxiety and adverse personal relationship effects as a consequence of testing positive for HIV or HCV
- (vii) Sample may be from someone other than named participant

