13. APPENDICES

APPENDIX A: DISTRIBUTION FLOWCHART

APPENDIX B: TESTING FLOWCHART MAIN STUDY

APPENDIX C: RESULTS FLOWCHART MAIN STUDY

Title	Validation of dried blood spot sampling for the detection of HCV			
	RNA: A sub-study of the NSW Dried Blood Spot Self-Sampling HIV and Hepatitis C Testing Pilot Program.			
Background and Rationale	Declines in annual HCV RNA testing and treatment is threatening Australia's ability to meet the HCV Targets outlined in the Fifth National Hepatitis C Strategy and the NSW Health Hepatitis C Strategy (2022-2025). Increasing HCV testing is hampered by diagnostic pathways requiring multiple visits and loss to follow- up, amplified in key populations, such as people who inject drugs [1]. Stigma and discrimination associated with HCV and how it was acquired can be a barrier to testing and treatment initiation [2].			
	Dried Blood Spot (DBS) as an alternative sampling and testing option has been shown to increase testing and linkage to care [3,4]. It is valuable in settings where venepuncture is not available, when venous access is poor or where other barriers to accessing services may be present. Samples are produced from finger-stick collection of capillary whole-blood (50-100 μ l) onto specialised filter paper. Once dried, samples have good stability, are easy to store and do not require cold chain transport [5,6,7]. Collection of DBS samples does not require a trained clinician and can be performed by a lay person with minimal training [5].			
	Literature on HCV DBS testing has shown an overall sensitivity of > 97% and specificity >99% for diagnostic accuracy of HCV RNA [8,9,10] and sensitivity of >96% and specificity of >99% for HCV antibody [9,11].			
	There are currently no hepatitis C serological or molecular laboratory assays available within Australia that include DBS as a registered sample type and approved by the Therapeutic Goods Administration (TGA). Therefore, the NSW DBS Pilot was implemented as a research study under the TGA Clinical Trial Notification (CTN) Scheme.			
	The DBS sample type requires validation against paired venous sample in a National Association of Testing Authorities (NATA) Australia accredited laboratory, to provide the scientific evidence required by the TGA for approval of this device in routine clinical settings.			

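### Section 6.1 ties adverse-event recording to the HIV EIA, so DBS HCV testing and the venepuncture sub-study have no recording rule

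*Protocol*

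**What the plan says.** Section 6.1 states: "Any adverse events in this study related to the use of dried blood spot specimens with the 4th generation EIA test will be recorded". It names the HIV reference laboratory and the Project Coordinator as recorders. De-identified data go to the responsible ethics committee, and also to the principal investigators for review by the steering and working group. A second paragraph asks that participant wellbeing come first when any adverse event is managed, and sets up a separate complaints route.

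Elsewhere the protocol describes a wider study:

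- Section 5.12 identifies the EIA as the HIV test: "The HIV 4th generation EIA has a sensitivity of >99%, a specificity of >99% and window period of 15-21 days". It gives a different assay for hepatitis C: "HCV testing will use the Hologic Panther, Aptima HCV Quant Dx assay", a nucleic acid amplification test.
- Section 4.1 says that "the HIV and HCV tests will be separated out and offered to individuals based on meeting the eligibility criteria for each test".
- Section 5.11 adds a sub-study in which "participants will be asked to provide a paired sample of blood (5ml) collected via venepuncture by a healthcare professional". It is optional, enrols up to 1,300 people, and sends its samples to NSW Health Pathology.
- Section 5.14 lists as a study risk: "Bleeding, discomfort and bruising can occur from a finger prick test".
- The sub-study synopsis (Appendix D) notes: "There are currently no hepatitis C serological or molecular laboratory assays available within Australia that include DBS as a registered sample type". It adds that for this reason "the NSW DBS Pilot was implemented as a research study under the TGA Clinical Trial Notification (CTN) Scheme".

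**The concern.** The scope of a safety-recording rule should match what the study does to participants. This one names a single assay and reads as though written for an HIV-only programme. Followed to the letter, it does not require anyone to record a mislabelled HCV sample, a wrongly issued HCV result or an injury from venepuncture. Nor need such an event go to the ethics committee, the principal investigators or the steering group.

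The HCV use of dried blood spots is as off-label as the HIV use, by the protocol's own account, and the sub-study exists to supply validation data to the regulator. If section 6.1 is applied as written, a report of few or no adverse events would say nothing about the HCV procedures or the venepuncture. A reader of that report could not tell this.

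**Working it through.** No arithmetic decides this point. The check is whether each procedure or risk in the protocol meets the condition in section 6.1, namely a link to DBS specimens used with the 4th generation EIA.

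**Step 1: what the EIA is.** Section 5.12 describes it as an HIV test. Section 7 (outcome 2) uses the count of these tests as the denominator for HIV positivity, while outcome 3 uses HCV RNA tests. The term therefore does not extend to HCV.

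**Step 2: each procedure against the rule.**

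| Procedure | Where described | Within 6.1? |
|---|---|---|
| DBS HIV testing | 5.12 | Yes |
| DBS HCV RNA testing, Aptima assay | 5.12 | No; not an EIA |
| HCV-only participation | 4.1 | No; that person's sample has no HIV EIA |
| Venepuncture, 5 ml, up to 1,300 people | 5.11 | No; not a DBS specimen |
| Sub-study DBS assays (Cobas HCV RNA, Alinity i Anti-HCV) | Appendix D, Testing | No; neither is the HIV EIA |
| Finger prick, HIV or dual kit | 5.10, 5.14 (iii) | Not expressly; arguable |
| Finger prick, HCV-only kit or sub-study | 4.1, Appendix D | No |

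**Step 3: another rule elsewhere?** Sections 5.11 and Appendix D contain no adverse-event provision. Section 5.14 lists risks but no recording duty, and does not list venepuncture. It describes risks (iv) to (vii) as ones that routine practice also carries. Risk (iii), the finger prick, is not in that group.

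**Step 4: does the rest of 6.1 widen the scope?** The sentence on de-identified data governs where recorded events are sent. The sentence on any adverse event governs how events are managed. Neither changes which events must be recorded.

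**Step 5: who records.** The two recorders are the HIV reference laboratory and the Project Coordinator. Sub-study samples go to a different laboratory. Under section 5.3, a Phase 2 site that delivers its own results carries clinical governance for them. Section 6.1 gives no explicit duty to that laboratory, the sub-study clinics or the Phase 2 sites.

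**Step 6: extent.** The sample-size plan (synopsis and section 9) has 860 HIV tests plus 1,000 dual HIV/HCV tests: 860 + 1,000 = 1,860. All 1,860 include the HIV EIA and are within the rule for that part. The HCV part of the 1,000 dual tests is outside it, as are up to 1,300 venepunctures and any HCV-only tests, for which no number is given.

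**The case against.** The strongest reply is that this is a drafting lag with several backstops. Complaints about the pilot, whatever the assay, go to the principal investigators and the ethics committee. Distressed participants can reach a nurse. Validation codes are checked before testing and again before release. The Project Coordinator already liaises with site staff, and naming two recorders does not bar others from passing events to them. These points are fair, but none is a recording rule. The complaints route works only if a participant complains, and it will not capture what a laboratory or clinic sees.

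A reader might infer four stronger things that the documents do not support:

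- **That most of the study goes uncounted.** Every test in the sample-size plan includes the HIV EIA, and the volume of HCV-only testing is not stated.
- **That finger-prick events are never recordable.** For HIV and dual kits, collecting the specimen can reasonably be read as part of its use with the EIA. Not expressly covered is the accurate description there.
- **That the Aptima specificity of 98.6% in section 5.12 gives a count of missed events** (1 − 0.986 = 0.014, or 14 per 1,000 uninfected people tested). That figure is not stated to be for dried blood spots; Appendix D cites above 99% and assumes 99%. False positives expected from imperfect specificity are also a performance outcome, which the study measures separately. The protocol does not class them as adverse events.
- **That delayed results should be reportable events.** Nothing in the conflict between these sections concerns delay.

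**Conclusion.** The point holds in a limited form. Section 6.1 states a recording rule whose scope does not match the current study. DBS HCV RNA testing, including HCV-only participants, and the venepuncture sub-study are outside it. Finger-prick events are clearly outside for HCV-only kits and the sub-study, and not expressly covered otherwise. No explicit recording duty reaches the sub-study laboratory, the sub-study clinics or Phase 2 sites.

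This rests on reading 6.1 literally and on finding no other adverse-event rule in the protocol. It is not a detail that could be left to a statistical analysis plan, because the protocol itself fixes which events are recorded and by whom. The size can be given only as exposure: the HCV part of 1,000 planned dual tests, up to 1,300 optional venepunctures, and an unstated number of HCV-only tests. The physical risks that the protocol lists are minor (bleeding, discomfort and bruising). No sample size, power or analysis figure changes. It should be corrected because the gap is in safety oversight and closing it costs little.

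**What to change.** Reword section 6.1 so that it covers adverse events related to any study procedure: capillary collection, venepuncture, and DBS testing for HIV or HCV, including mislabelled samples and incorrectly issued results. State that the sub-study laboratory, the sub-study clinics and the Phase 2 sites report such events to the Project Coordinator, who passes them on by the existing route. Reconcile 6.1 with sections 5.11, 5.12, 5.14 and Appendix D so that the listed procedures and risks match the recording rule.

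The cost is one paragraph in the next amendment and a few more event forms. The reported event count will rise slightly, so reports that span the change should say when the wider rule began.

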7. EVALUATION OUTCOMES AND DEFINITIONS

The key study outcomes and their definitions are listed below

- 1. **Return rate:** proportion of DBS samples which were returned for testing. This will also be disaggregated by target population.
- 2. **HIV test positivity rate:** The numerator for calculating HIV positivity is the number of laboratory confirmed HIV positive individuals with Western Blot testing. The denominator is the number of individual 4^{thd} generation EIA tests performed during the pilot period.
- 3. **HCV test positivity rate:** The numerator for calculating HCV positivity is the number of laboratory confirmed HCV positive individuals with RNA testing on the Hologic Panther analyser. The denominator is the number of individual HCV RNA tests performed during the pilot period.
- 4. **Proportion of participants who are infrequent testers:** The proportion of DBS participants who reported at the first registration they had never tested for HIV before or had tested over 2 years

ago. This outcome measure will also be disaggregated by target population and test combination (HIV only compared to HIV/HCV dual testing).

- 5. Linkage to care rate: proportion of DBS participants who return an HIV detected test result and are reviewed by a referral clinician within 2 weeks of diagnosis. Linkage to care will be verified by the registered nurse making the follow-up call to newly diagnosed participants one week after notification of results, and information will be self-reported by the participant. Linkage to care will be reported separately for participants who receive a reactive HIV result, and those who receive a reactive HCV RNA test result.
- 6. **Mean CD4 count at diagnosis:** calculated in laboratory confirmed HIV positive individuals using flow cytometry
- 7. Re-testing rate: Proportion of DBS participants who had two or more DBS tests in the study period
- 8. Acceptability of DBS test process: Proportion of DBS participants who reported they found the DBS testing processed acceptable or highly acceptable
- 9. Cost per DBS test conducted: the costs to the health system of each DBS test done
- 10. **Cost per HIV infection diagnosed** by DBS test: the costs to the health system of each positive DBS test
- 11. **Cost per HCV infection diagnosed** by DBS test: the costs to the health system of each positive DBS test

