Dried blood spot (DBS) is a self-collection method (rather than a self-test) and enables people to collect samples in their own home, post back and receive results without having to attend a health service. Additionally, as a blood sample is collected (rather than oral fluid) acute infections are more likely to be detected and the blood sample enables screening and confirmation to occur using the same sample. DBS testing offers significant advantages when compared to conventional venous blood samples, particularly in relation to logistics such as the transportation of samples to central testing laboratories and in settings where laboratory infrastructure may be limited. DBS offers opportunities for transport because the biological hazards related to liquid samples are mitigated by drying the sample and providing supplementary packaging to contain samples in transit. Appropriately collected and processed samples lend themselves to a postal type distribution network which may improve convenience for participants and increase uptake and frequency of HIV testing.

DBS collection for conventional HIV serological testing has been successfully applied for decades in early infant diagnosis of HIV and in monitoring prevalence of HIV among child-bearing women and injecting drug users (19). There are international quality assurance programs to assess the performance of laboratories conducting testing of DBS samples.

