A trained clinical nurse specialist from SHIL will speak to participants about having a confirmatory venous HIV or Hepatitis C test done and will provide advice about where participants can go for testing, such as local public sexual health clinics, GPs, or relevant clinicians in the HIV Support Program run by the Ministry of Health where appropriate. Where SHIL is delivering results on behalf of a registered site, nurses will ask the client for permission to provide this result to the associated site for assistance in engaging the client in confirmatory testing, treatment and ongoing care. Procedures for referral and booking of participants for follow-up care are outlined in the DBS Results Management Business Rule. As part of this pilot, SHIL will routinely follow-up all participants (or the relevant site) with a detectable HIV result one week after notification to ensure they have attended testing, been linked to care and offer further referrals if required.

All participants who return a detectable HIV result will be actively contacted on 5 attempts, as per recommended guidelines in the DBS results management Business Rule. If contact remains unsuccessful, the Project Coordinator and clinical governance lead at Sydney Sexual Health Centre will be alerted for follow-up.

During Phase 2, a setting/site may request to provide results directly to participants. In this situation, SHIL will provide results to a clinician at the site. The site will then provide the results to the participants. In the case of a suspected new positive HIV result, SHIL will follow up with the site to ensure that results have been provided and linkage to care has been supported. Information on participants' treatment initiation will be collected from sites via a standardised case report form. For new HIV cases, sites will confirmatory follow up venous test results (HIV), CD4 results (HIV) and information on linkage to care and treatment initiation to SHIL or the DBS Study Coordinator, and SHIL will ensure all confirmatory results are forwarded to the NSW State Reference Laboratory for HIV (St Vincent's Hospital Sydney). A specific consent process has been developed for participants to consent to site delivery of results. (Approved in amendment 6 application).

See Appendix C for the test results flowchart.

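### Outcome 2 admits an HIV positive only on Western Blot, although sections 5.12 and 5.14 allow confirmation by other tests

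*Protocol*

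**What the plan says.** **The outcome.** Protocol section 7, outcome 2, defines the numerator of the HIV positivity rate: "The numerator for calculating HIV positivity is the number of laboratory confirmed HIV positive individuals with Western Blot testing". The denominator is a count of fourth "generation EIA tests performed during the pilot period".

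**The laboratory procedures.** Section 5.12 screens with an "HIV antigen/antibody combo assay" and runs a Western Blot on samples that react. It then says that a reference laboratory can apply several supplemental tests to confirm that a positive is true, and adds: "This testing may also include TGA approved nucleic acid tests for HIV". Section 5.14, risk (ii), holds back a reactive result until a validated confirmatory test has been done, and gives Western Blot as an example of such a test.

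**The venous test.** Under section 5.13 a nurse discusses a confirmatory venous test with each person who has a detected result. The method of that test is not specified. For new HIV cases at Phase 2 sites that give their own results, "SHIL will ensure all confirmatory results are forwarded to the NSW State Reference Laboratory for HIV".

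**The other HIV outcomes.** Outcome 5 refers to a detected and then to a reactive HIV result. Outcome 6 (CD4) refers to laboratory confirmation without naming a test. Outcome 10 (cost per diagnosis) refers to a positive DBS test.

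**The concern.** The counting rule is narrower than the confirmation pathway of the same protocol. The people affected are those who react on the antigen/antibody screen, are negative or indeterminate on Western Blot, and are confirmed by another test that section 5.12 permits. A typical member of this group would be someone early in infection, because Western Blot detects antibody and the screen also detects antigen. That is general laboratory knowledge and is not stated in the protocol.

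At stake is the HIV yield of the program. Section 1.2 gives earlier diagnosis and less onward transmission as the purpose, so early cases are ones the evaluation would want to see. Few positives can be expected, so one person counted differently moves the rate visibly. HIV positivity belongs to a secondary objective and carries no target or power calculation, which limits the consequence.

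**Working it through.** **Text check**

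| Place in the protocol | What confirms an HIV positive |
|---|---|
| Section 7, outcome 2 | Western Blot; nothing else named |
| Section 5.12 | Western Blot on reactive samples; supplemental tests, including nucleic acid tests, may also be used |
| Section 5.14, risk (ii) | A validated confirmatory test, with Western Blot as an example |
| Section 5.13 | Confirmatory venous test, method not given |

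Take a person who reacts on the screen, is Western Blot indeterminate, and is positive on a supplemental nucleic acid test. Sections 5.12 and 5.14 allow this person to be treated as confirmed. Outcome 2, read literally, does not count them. It also does not say which specimen the Western Blot must be run on, or how an unresolved reactive sample is classified.

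**Size (illustration only)**

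The protocol states no expected HIV positivity, so there is no planned figure to reproduce. Inputs:

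- UK pilot, section 1.1: 17,629 kits requested, 59% returned, 146 diagnoses.
- Number of tests, section 3.2: 860 (Phase 1 minimum number of participants) and 1,860 (total). Both are used as if each were one HIV test.
- f, the share of true infections that Western Blot does not confirm: not in the documents, assumed to be 0% to 20%.

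Positivity: 0.59 × 17,629 = 10,401 returned kits; 146 / 10,401 = 1.40%.

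Counted cases = tests × 1.404% × (1 − f). Positivity = 1.404% × (1 − f).

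| f (assumed) | Positivity | Cases per 860 | Lost | Cases per 1,860 | Lost |
|---|---|---|---|---|---|
| 0% | 1.40% | 12.1 | 0 | 26.1 | 0 |
| 5% | 1.33% | 11.5 | 0.6 | 24.8 | 1.3 |
| 10% | 1.26% | 10.9 | 1.2 | 23.5 | 2.6 |
| 20% | 1.12% | 9.7 | 2.4 | 20.9 | 5.2 |

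The relative understatement equals f. One person among 12 is 1/12 = 8.3% of the yield.

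**The case against.** The strongest reply is that this is a loosely worded line and not a deliberate exclusion. Western Blot is the one confirmatory test that section 5.12 applies to reactive samples as a matter of routine, while nucleic acid testing is optional. A uniform criterion is a defensible choice for an outcome that is to be stratified by pathway. The Appendix B flowchart is not shown and may cover indeterminate samples. The early-infection share is assumed, and even at its upper end few cases are involved.

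Much of this stands. The size is small and uncertain, and a Western Blot-only count has value as a uniform figure. Appendix B, however, is a testing flowchart, and the counting rule sits in section 7. The protocol itself fixes that rule more narrowly than its own procedures, so this is not detail left to an analysis plan.

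The documents do not support several stronger readings that a reader might infer:

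- **That venous-confirmed cases are necessarily left out.** Outcome 2 does not restrict the Western Blot to the DBS sample, and the venous method is unspecified. A venous Western Blot could bring the person into the numerator.
- **That a case contradicted by the venous test necessarily stays in.** The text is silent, and the requirement of laboratory confirmation can be read to exclude such a person.
- **That the same restricted count feeds CD4 and cost per diagnosis.** Outcomes 6 and 10 are worded differently and do not carry the Western Blot limit.
- **That the outcome defeats the stated rationale of catching acute infection.** Section 1.1 says: "as a blood sample is collected (rather than oral fluid) acute infections are more likely to be detected". It credits the specimen type, not the antigen component of the assay. Only early cases not yet positive on Western Blot are affected, not acute infections as a class.

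**Conclusion.** The mismatch is real. Outcome 2 names Western Blot as the only entry to the numerator, while sections 5.12 and 5.14 accept other validated confirmation. Read literally, a person confirmed by nucleic acid testing but not by Western Blot is left out of HIV positivity.

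The effect cannot be fixed from the documents. It is 0 to about 2.4 of roughly 12 positives per 860 tests, assuming that the UK positivity carries over and that 0% to 20% of true infections are not Western Blot confirmed. The protocol does not say how the UK pilot confirmed its diagnoses, so 1.40% serves only for scale. The conclusion about the definition rests on the text and not on this arithmetic.

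**What to change.** 1. Define the outcome 2 numerator as people reactive on EIA and confirmed by Western Blot or by another validated confirmatory test in the laboratory algorithm, such as a nucleic acid test.
2. Report the Western Blot-only count beside it, so that a uniform figure remains available.
3. Report the number of reactive people left unresolved, meaning Western Blot negative or indeterminate with no further confirmatory result.
4. Report venous results that add or contradict a case separately by pathway. Their return is stated only for Phase 2 sites that deliver their own results, so folding them into the main count could make the case definition differ between pathways.
5. State which case definition outcomes 6 and 10 use.

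The cost is one reworded definition, one extra count and an unresolved category in the report. No new test is needed. The change concerns counting only and leaves the release of results and clinical follow-up as they are.
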